7.4.3.1.2. Nonhematologic Toxicity

Specific guidelines for dose adjustments in patients who experience olaratumab-related IRRs may be found in Section [7.8.1](#).

[Table JGDR.10](#) shows olaratumab dose modifications that should be made for nonhematologic toxicities judged as potentially related to olaratumab in combination with doxorubicin, ifosfamide and mesna and that have recurred despite 1 reduction in doxorubicin, ifosfamide and mesna dose.

Table JGDR.10. General Guidelines for Olaratumab Dose Modification due to Nonhematologic Toxicities

Grade	Required Dose Modification
Grade 1	No dose modification is required.
Grade 2	At the investigator's discretion, the patient may continue to receive olaratumab at the full dose, provided the event does not pose a serious health risk or is easily treated.
Grade 3 and 1 reduction in doxorubicin, ifosfamide and mesna doses has already occurred	
If not adequately controlled with appropriate supportive care, withhold dose until \leqGrade 1 or has returned to pretreatment baseline.
 
Treatment may resume as follows:
 
 • 15-mg/kg Dose Level: Reduce dose to 12 mg/kg • 20-mg/kg Loading Dose Cycle Level: Reduce dose to 15 mg/kg 
If toxicity recurs after therapy resumes, discontinue combination therapy (olaratumab + doxorubicin/ifosfamide/mesna). Patients who have not progressed will receive olaratumab as monotherapy until there is evidence of disease progression, death, intolerable toxicity, or other withdrawal criteria are met.

Grade 4 and 1 reduction in doxorubicin, ifosfamide and mesna doses has already occurred	
Withhold dose until toxicity is \leqGrade 1 or has returned to pretreatment baseline.
 
Permanent discontinuation of olaratumab should be considered for any patient experiencing Grade 4 nonhematologic toxicity assessed as related to olaratumab.
 
However, if resumption of dosing is deemed appropriate by the investigator, treatment may resume only after consultation with the Lilly CRP as follows:
 
 • 15-mg/kg Dose Level: Reduce dose to 12 mg/kg • 20-mg/kg Loading Dose Cycle Level: Reduce dose to 15 mg/kg 
If toxicity recurs after therapy resumes, discontinue combination therapy (olaratumab + doxorubicin/ifosfamide/mesna). Patients who have not progressed will receive olaratumab as monotherapy until there is evidence of disease progression, death, intolerable toxicity, or other withdrawal criteria are met.

7.4.3.2. Doxorubicin Dose Modifications

Dose modifications of doxorubicin will follow the guidelines outlined below and may be adjusted according to local standard of care and label.

7.4.3.2.1. *Hematologic Toxicity*

Doxorubicin will not be administered after the initial dose if the patient's ANC is <1500 cells/ μ L or if the platelet count is $<100,000$ cells/ μ L. When necessary, the next treatment cycle should be delayed until the ANC is ≥ 1500 cells/ μ L and the platelet count is $\geq 100,000$ cells/ μ L and any nonhematologic toxicities have resolved. For patients who experience \geq Grade 3 neutropenic fever or infection or Grade 4 neutropenia without fever lasting more than 1 week, doxorubicin should be reduced to 75% of the starting dose (that is, to approximately 60 mg/m^2). If a patient experiences a second incidence of neutropenic fever/infection or has another episode of Grade 4 neutropenia lasting >1 week, then a second dose reduction to 45 mg/m^2 should occur.

Therapeutic and prophylactic use of pegfilgrastim or other G-CSFs is required per current American Society of Clinical Oncology (ASCO; Smith et al. 2006) and National Comprehensive Cancer Network (NCCN) guidelines (NCCN 2014). In general, G-CSF products like filgrastim or pegfilgrastim should be administered approximately 24 hours after the completion of cytotoxic chemotherapy (for example, on Day 5 for patients in full-dose ifosfamide cohorts or Day 4 for patients in reduced-dose ifosfamide cohorts). For patients with Grade 4 ANC without fever/infection lasting less than 1 week, re-treatment will be allowed at the investigator's discretion with the full dose of doxorubicin (75 mg/m^2) with required use of G-CSFs per current ASCO guidelines (Smith et al. 2006). See [Table JGDR.11](#) for doxorubicin dose modification for neutropenia.

Table JGDR.11. General Guidelines for Doxorubicin Dose Modification Due to Neutropenia

Toxicity	Required Dose Modification
ANC <1500 cells/ μ L	No doxorubicin administered; entire treatment cycle delayed.
At re-treatment: If \geq Grade 3 neutropenic fever/infection has occurred	Approximately 60 mg/m ² doxorubicin.
If Grade 4 neutropenia lasting longer than 1 week has occurred	Approximately 60 mg/m ² doxorubicin.
If Grade 4 neutropenia without fever/infection lasting less than 1 week has occurred	Retreatment with doxorubicin at full dose at investigator's discretion with required use of G-CSFs.
Second incidence of either: 1) \geq Grade 3 neutropenic fever/infection 2) Grade 4 neutropenia lasting longer than 1 week	Second dose reduction to 45 mg/m ² .
Third incidence of either: 1) \geq Grade 3 neutropenic fever/infection 2) Grade 4 neutropenia lasting longer than 1 week	Discontinue combination therapy (olaratumab + doxorubicin/ifosfamide/mesna) and follow per Section 7.4.2.

Abbreviations: ANC = absolute neutrophil count; G-CSF = granulocyte-colony-stimulating factor.

7.4.3.2.2. Nonhematologic Toxicity

Permanent discontinuation of doxorubicin should be considered for any patient experiencing Grade 4 nonhematologic toxicity assessed as related to doxorubicin. If the investigator feels re-dosing of doxorubicin is appropriate (except for Grade 4 cardiotoxicities, which require mandatory discontinuation (see Section 7.4.3.2.3), treatment may only resume after consultation with the Lilly CRP, with the dose reduced to 60 mg/m² (or less if agreed by the investigator and Lilly CRP). If Grade 4 nonhematological toxicity recurs after therapy resumes, doxorubicin (in combination with ifosfamide and mesna) will be permanently discontinued and the patient will be followed as outlined in Section 7.4.2.

For appropriate management of cardiac toxicities, refer to Section 7.4.3.2.3.

7.4.3.2.3. Monitoring for Doxorubicin-Associated Cardiotoxicity

Cardiotoxicity is a recognized risk of doxorubicin that increases with higher cumulative drug exposure. Cardiac monitoring is conducted by a combination of monitoring of clinical parameters, ECG, and echocardiogram (ECHO)/multiple-gated acquisition (MUGA) scan.

Changes in ECG, arrhythmias, tachycardia and/or chest pain should be managed based on the specific findings.

Patients will undergo baseline LVEF determination using ECHO or MUGA scan. This evaluation may be repeated at any time during the study if clinically indicated. A decrease in LVEF of \geq 10% and below the lower limit of normal, or an absolute decrease of 20%, or if the absolute LVEF decreases to or below 40%, then doxorubicin will be discontinued. Doxorubicin should also be discontinued if the patient develops Grade 3 or 4 left ventricular systolic dysfunction (symptomatic congestive heart failure).

The diagnostic method used at baseline for cardiovascular assessments (for example, ECHO or MUGA scans) should be the same method used throughout the study, unless there is clinical or instrumental evidence that further investigations are needed.

7.4.3.3. Ifosfamide Toxicities and Dose Modifications

Dose modifications of ifosfamide will follow the guidelines outlined below and may be adjusted according to local standard of care and label. Two reductions in ifosfamide dose for toxicity will be permitted during the study. If a third dose reduction is necessary, the patient will be discontinued from the combination therapy (olaratumab + doxorubicin/ifosfamide/mesna) and followed as outlined in Section 7.4.2.

General guidelines for ifosfamide dose modification are shown in Table JGDR.12. Dose modifications of ifosfamide due to hepatic impairment are shown in Table JGDR.13.

Table JGDR.12. General Guidelines for Dose Modification of Ifosfamide due to Toxicity

Worst Toxicity/Counts in Previous Cycle	Ifosfamide Dose Reduction ^a
Febrile neutropenia	First episode: Maintain full dose Subsequent episodes: Decrease 20%
Platelets <75,000/mm ³	If less than 1 week duration: Maintain full dose If greater than 1 week duration: Decrease 20%
Thrombocytopenic bleeding	Decrease 20%
Somnolence or other signs of encephalopathy	Discontinue combination therapy (olaratumab + doxorubicin/ifosfamide/mesna) and follow per Section 7.4.2. Administer methylene blue 50 mg intravenously every 4 hours until resolution.
Grade 3 or 4 neurotoxicity other than encephalopathy	Discontinue combination therapy (olaratumab + doxorubicin/ifosfamide/mesna) and follow per Section 7.4.2.
Grade 3 related organ toxicity/nonhematologic	Decrease 20%
Grade 4 related organ toxicity/nonhematologic	Discontinue combination therapy (olaratumab + doxorubicin/ifosfamide/mesna) and follow per Section 7.4.2.

Abbreviation: mg = milligrams.

^a Do not re-treat until criteria in Section 7.4 are met.

Table JGDR.13. Dose Modification of Ifosfamide due to Hepatic Impairment

Bilirubin	and/or	AST/ALT	Ifosfamide Dose Reduction ^a
1-2 × ULN		<2 × ULN	Full dose
2-4 × ULN		2-5 × ULN	75% of initial dose
>4 × ULN		>5 ULN	Discontinue combination therapy (olaratumab + doxorubicin/ifosfamide/mesna) and follow per Section 7.4.2.

Abbreviations: ALT = alanine aminotransferase; AST = aspartate aminotransferase; ULN = upper limit of normal.

^a Based on clinical judgment – less conservative adjustments can be considered if hepatic changes are secondary to metastases rather than hepatic cirrhosis or hepatitis.

7.4.3.3.1. Ifosfamide-Associated Central Nervous System Toxicity

Central nervous system toxicity appears to be dose dependent, and is variable in onset, but usually resolves when ifosfamide is discontinued. Incidence is higher with higher doses, concomitant use of aprepitant, electrolyte imbalances, renal/hepatic impairment, or preexisting CNS disorders. It may manifest as transient mental status changes (somnolence, confusion, hallucination, disorientation and lethargy), cerebellar dysfunction, extrapyramidal symptoms, transient weakness, cranial nerve dysfunction, or seizure activity. Methylene blue, which may act as an electron acceptor or decrease chloroacetaldehyde formation, has been suggested as treatment or prophylaxis for ifosfamide-induced encephalopathy. Due to the potential for additive effects, drugs acting on the CNS (such as antiemetics, sedatives, narcotics, or antihistamines) must be used with particular caution or, if necessary, be discontinued in case of ifosfamide-induced encephalopathy.

7.4.3.3.2. Ifosfamide-Associated Urotoxic Effects

The incidence of urotoxic effects without an uroprotector can be up to 40% and is dose dependent; coadministration of mesna and adequate hydration are mandatory in this study. Patients may present with hematuria, symptomatic cystitis, or bladder fibrosis. Past or concomitant radiation of the bladder or busulfan treatment may increase the risk of hemorrhagic cystitis. Several methods of treatment for established hematuria have been described: bladder irrigation with water or normal saline, intravesical instillation of astringents (alum, silver nitrate), systemic administration of antifibrinolitics (aminocaproic acid, tranexamic acid), cystoscopy to evacuate the bladder of clots, continuous bladder irrigation and intravesical prostaglandins. For severe or refractory hematuria, intravesical formalin, phenol, or prostaglandin has been used with or without surgical intervention (electrocautery, cryosurgery, diversion of urine flow, hypogastric artery ligation, or cystectomy). Discontinuation or dose reduction of ifosfamide should follow local standard of care and label for patients with macroscopic hematuria.

7.4.3.3.3. *Ifosfamide-Associated Proximal Tubular Damage*

Glomerular, proximal, or distal tubular impairment may all occur, often in combination and may progress even after ifosfamide has been discontinued. Proximal tubular damage often presents as Fanconi syndrome with low serum bicarbonate, proteinuria, glucosuria, aminoaciduria and hypochloremic metabolic acidosis. Risk factors for the development of nephrotoxicity include preexisting renal impairment, concurrent use of nephrotoxic drugs, reduced renal reserve (unilateral nephrectomy), hydronephrosis and total cumulative dose. Renal impairment may increase the risk of myelosuppression and possibly, cardiotoxicity. Mesna does not appear to be protective against the proximal tubular abnormalities induced by ifosfamide. Dose modifications guidelines of ifosfamide due to renal impairment are shown in [Table JGDR.14](#).

Table JGDR.14. Dose Modification of Ifosfamide due to Renal Impairment

Creatinine Clearance (mL/min) ^a	Ifosfamide Dose Reduction
>60	Full dose
40-60	Reduce to 75% of initial dose
20-40	Reduce to 50% of initial dose
<20	Discontinue combination therapy (olaratumab + doxorubicin/ifosfamide/mesna) and follow per Section 7.4.2 .

Abbreviations: min = minutes; mL = milliliters.

^a Calculated using Cockcroft and Gault formula (see [Appendix 6](#)).

7.5. Packaging and Labeling

7.5.1. Olaratumab

Olaratumab will be provided to study sites by Lilly. Clinical trial materials will be labeled according to the country's regulatory requirements.

Olaratumab will be supplied as a sterile preservative-free solution for IV infusion in single-use vials containing 500 mg/50 mL of olaratumab (10 mg/mL).

Olaratumab is formulated in 10 mM histidine, 100 mM glycine, 50 mM sodium chloride, 75 mM mannitol and 0.02% polysorbate-20, with a pH of 5.5. All excipients used in the formulation of olaratumab drug product are of pharmacopoeia grade.

Clinical study materials will be labeled according to the country's regulatory requirements.

7.5.2. Doxorubicin, Ifosfamide and Mesna

Where commercially available, doxorubicin, ifosfamide and mesna will be purchased by the sites. In the event that there are regional restrictions or supply limitations, doxorubicin, ifosfamide and/or mesna may be provided to the sites by Lilly.

Clinical study materials will be labeled according to the country's regulatory requirements.

7.5.3. Granulocyte-Colony Stimulating Factors

G-CSFs will be purchased by the sites.

7.5.4. Dexrazoxane

Where commercially available, dexrazoxane will be purchased by the sites. In the event that there are regional restrictions or supply limitations, dexrazoxane may be provided to the sites by Lilly.

Clinical study materials will be labeled according to the country's regulatory requirements.

7.6. Preparation/Handling/Storage/Accountability

7.6.1. Olaratumab

Olaratumab drug product must be stored under refrigeration at 2°C to 8°C (36°F-46°F) with protection from direct light. Do not freeze and/or shake olaratumab drug product. Stability studies have demonstrated that the drug product can withstand transient excursion to room temperature without adverse effect; however, storage at this temperature is not recommended.

Please refer to the Pharmacy Manual for information on preparing the olaratumab dosing solution for infusion.

7.6.2. Doxorubicin

Investigators should consult the approved doxorubicin hydrochloride package insert for complete preparation, handling and storage requirements. If a patient should have an IRR to doxorubicin, the investigator should follow the manufacturer's recommendations and clinical guidelines in the management of the patient.

Doxorubicin is administered as an IV infusion. Doxorubicin may be administered either as a bolus over 60 minutes or less, or as a 24-hour continuous infusion, depending on institutional protocol.

If erythematous streaking along the vein proximal to the site of infusion or facial flushing occur, decrease the rate of doxorubicin administration.

Doxorubicin must be reconstituted prior to infusion. The reconstituted solution is stable for 7 days at room temperature and under normal room light and 15 days under refrigeration (2°C to 8°C). It should be protected from exposure to sunlight.

Parenteral drug products should be inspected visually for particulate matter and discoloration prior to administration, whenever solution and container permit.

7.6.3. Ifosfamide

Investigators should consult the approved ifosfamide package insert for complete preparation, handling and storage requirements.

Ifosfamide single-dose vials should be stored at controlled room temperature from 20°C to 25°C (68°F to 77°F) and protected from temperatures above 30°C (86°F).

Exercise caution while handling ifosfamide. The handling and preparation of ifosfamide should always be in accordance with current guidelines on safe handling of cytotoxic agents. Several

guidelines on this subject have been published (OSHA 1999; NIOSH 2004; ASHP 2006; Polovich et al. 2014). Skin reactions associated with accidental exposure to ifosfamide may occur. To minimize the risk of dermal exposure, always wear impervious gloves while handling vials and solutions containing ifosfamide. If ifosfamide solution contacts the skin or mucosa, immediately wash the skin thoroughly with soap and water or rinse the mucosa with copious amounts of water.

7.6.4. Mesna

Investigators should consult the approved mesna package insert for complete preparation, handling and storage requirements.

Mesna injection solution should be stored at 20°C to 25°C (68°F to 77°F), with excursions permitted to 15°C to 30°C (59°F to 86°F).

7.7. Treatment Compliance

The study medication will be administered only at the investigational sites by the authorized study site personnel. As a result, treatment compliance is ensured.

7.8. Concomitant Therapy and Supportive Care

7.8.1. Olaratumab Infusion-Related Reactions

As with other monoclonal antibodies, hypersensitivity reactions may occur during or following olaratumab administration.

A 1-hour observation period is required after the administration of olaratumab in the first and second cycles. If there is no evidence of an IRR during the initial 2 cycles of olaratumab, then no observation period is required for subsequent treatment cycles. In the event that a Grade 1 or 2 IRR occurs after Cycle 2, the 1-hour observation period will be reinstated for a minimum of 2 cycles. The reinstated observation period may be suspended after 2 cycles if the patient shows no further signs or symptoms of an IRR. During the observation period, patients treated with olaratumab should be closely monitored for signs and symptoms indicative of an IRR by the medical staff from the start of the infusion until at least 1 hour after the end of the infusion in an area where emergency medical resuscitation equipment and other agents (epinephrine, prednisolone equivalents, etc.) are available.

Treatment guidelines for olaratumab IRRs as well as premedications for subsequent infusions are described in [Table JGDR.15](#).

Olaratumab infusion reactions will be defined according to the NCI-CTCAE Version 4.0 definition of IRRs.

Symptoms occurring during or following infusion of investigational therapy may also be defined according to AE categories such as allergic reaction, anaphylaxis, or cytokine release syndrome (NCI-CTCAE Version 4.0 Section “Immune system disorders”). In the setting of symptoms occurring during or following infusion of investigational therapy, investigators are encouraged to

use the AE term “infusion-related reaction” and any additional terms (including those not listed here) that best describe the event.

Table JGDR.15. Olaratumab Infusion-Related Reaction Treatment Guidelines

NCI CTCAE Grade	Treatment	Premedication at Subsequent Infusions
Grade 1 or 2	
Stop infusion and monitor symptoms. Additional appropriate medical therapy should be given according to standard medical practice; may include, but is not limited to:
 
 • antihistamines (for example, diphenhydramine HCl) • steroids (for example, dexamethasone) • acetaminophen • oxygen 
After recovery, the infusion rate should be decreased 50% for the duration of the infusion.
	Patients should be premedicated with antihistamines, steroids, acetaminophen, etc., as appropriate.
Grades 3 or 4	
Stop infusion. Administer immediate treatment; may include, but is not limited to:
 
 • epinephrine • bronchodilators and/or glucocorticoids for symptomatic bronchospasm • IV fluids and/or pressors for hypotension 
Treatment with olaratumab should be immediately and permanently discontinued.
	No subsequent dosing

All attempts should be made to obtain an anti-olaratumab antibody and olaratumab PK blood samples as close to the onset of the event as possible, at the resolution of the event and 30 days (± 3 days) following the event. The procedure for sample collection and handling is described in a separate procedural manual.

Appropriate resuscitation equipment should be available in the room and a physician readily available during the period of drug administration.

Abbreviations: HCl = hydrochloride; IV = intravenous; NCI CTCAE = National Cancer Institute-Common Terminology Criteria for Adverse Events.

7.8.2. Granulocyte-Colony-Stimulating Factors and Erythroid Growth Factors

Because the doxorubicin, ifosfamide and mesna regimen is known to be highly suppressive of the bone marrow, G-CSFs such as pegfilgrastim must be used at each cycle and should be

administered according to ASCO guidelines (Smith et al. 2006) and NCCN guidelines (NCCN 2014). In general, G-CSF products like filgrastim or pegfilgrastim should be administered approximately 24 hours after the completion of cytotoxic chemotherapy (for example, on Day 5 for patients in full-dose ifosfamide cohorts or Day 4 for patients in reduced-dose ifosfamide cohorts). Erythroid-stimulating factors (such as erythropoietin) may be used at the discretion of the investigator and should also be administered according to ASCO and NCCN guidelines.

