Administer mesna	X	X	X	X					See Section 7.1.3 for details of mesna administration.
G-CSF	X								The use of G-CSFs is required. Administer according to ASCO and NCCN guidelines. In general, G-CSF products like filgrastim or pegfilgrastim should be administered approximately 24 hours after the completion of cytotoxic chemotherapy (for example, on Day 5 for patients in full-dose ifosfamide cohorts or Day 4 for patients in reduced-dose ifosfamide cohorts).
Sample collection									For all sample collection, see Appendix 4.
Pharmacodynamics									
Pharmacokinetics									
Immunogenicity									
Pharmacogenetics									
Other biomarkers									

Abbreviations: AE = adverse event; ASCO = American Society of Clinical Oncology; BSA = body surface area; C = cycle; CTCAE = Common Terminology Criteria for Adverse Events (NCI 2009); D = day; ECG = electrocardiogram; ECOG = Eastern Cooperative Oncology Group (Oken et al. 1982); G-CSF = granulocyte-colony stimulating factor; IRR = infusion-related reaction; IV = intravenously; LVEF = left ventricular ejection fraction; min = minutes; MUGA = multiple-gated acquisition; NCCN = National Comprehensive Cancer Network; PD = progressive disease; q = every; RBC = red blood cell; RECIST 1.1 = Response Criteria in Solid Tumors Version 1.1 (Eisenhauer et al. 2009).

^a Olaratumab monotherapy schedule applies to patients who have completed 6 cycles of olaratumab plus doxorubicin and ifosfamide and are continuing treatment with olaratumab monotherapy or have discontinued doxorubicin plus ifosfamide and are continuing with olaratumab monotherapy. Note: if a patient discontinues doxorubicin plus ifosfamide treatment prior to completing 6 cycles and is continuing treatment with olaratumab monotherapy, perform procedures according to the olaratumab monotherapy schedule beginning the next cycle after the patient discontinues doxorubicin/ifosfamide.

Table JGDR.3. Post-Treatment Follow-Up Schedule of Activities

Procedure	Short-Term Follow-Up ^a	Long-Term Follow-Up	Instructions
Visit	801	802-8XX	
Physical examination	X		Including weight and vital signs (temperature, blood pressure, pulse rate, respiration rate)
Concomitant medication	X		
AE collection	X		CTCAE Version 4.0.
ECOG performance status	X		

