7.1. Treatment Administered (Dosing Schedule)

Table JGDR.6 shows the treatment regimens. On days where multiple study drugs are to be administered, the drugs should be administered in the order shown in Table JGDR.6.

Table JGDR.6. Treatments Administered (Dosing Schedule)

Phase and Dose Cohort		Drug Name and Dose	Day of 21-day (± 3 days) cycle	Total dose	Route and duration of administration	Notes
Dose-Finding Phase	Olara 15 mg/kg	Olaratumab 15 mg/kg ^a	D1 and D8		IV over 60 (± 5) min Infusion rate should not exceed 25 mg/min	See Section 7.1.1 for premedication requirements and Section 7.8.1 for IRR monitoring period requirements
		Doxorubicin 25 mg/m ² per day ^a	D1, D2, D3	75 mg/m ²	IV over less than 60 min or continuous IV infusion (according to institutional practice)	Administer after olara on D1 and after any required observation period
		Ifosfamide 2.5 g/m ² per day ^a	D1, D2, D3, D4 ^b	10 ^b g/m ²	IV over 3 hours (± 15 min)	Administer after dox on D1, D2, D3
		Mesna dose \geq 60% of ifos dose ^a	D1, D2, D3, D4 ^b		According to institutional practice	
	Olara Loading Dose Cycle	Olaratumab 20 mg/kg Cycle 1 Olaratumab 15 mg/kg Cycles 2 to 6 ^a	D1 and D8 D1 and D8		IV over 60 (± 5) min Infusion rate should not exceed 25 mg/min	See Section 7.1.1 for premedication requirements and Section 7.8.1 for IRR monitoring period requirements
		Doxorubicin 25 mg/m ² per day ^a	D1, D2, D3	75 mg/m ²	IV over less than 60 min or continuous IV infusion (according to institutional practice)	Administer after olara on D1 and after any required observation period
		Ifosfamide 2.5 g/m ² per day ^a	D1, D2, D3, D4 ^b	10 ^b g/m ²	IV over 3 hours (± 15 min)	Administer after dox on D1, D2, D3
		Mesna dose \geq 60% of ifos dose ^a	D1, D2, D3, D4 ^b		According to institutional practice	
Dose Confirmation Phase	Recommended Olara Dose	Olaratumab dose determined from Dose-Finding Phase ^a	D1 and D8		IV over 60 (± 5) min Infusion rate should not exceed 25 mg/min	See Section 7.1.1 for premedication requirements and Section 7.8.1 for IRR monitoring period requirements
		Doxorubicin 25 mg/m ² per day ^a	D1, D2, D3	75 mg/m ²	IV over less than 60 min or continuous IV infusion (according to institutional practice)	Administer after olara on D1 and after any required observation period
		Ifosfamide 2.5 g/m ² per day ^a	D1, D2, D3, D4 ^b	10 ^b g/m ²	IV over 3 hours (± 15 min)	Administer after dox on D1, D2, D3

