		Mesna dose \geq 60% of ifos dose ^a	D1, D2, D3, D4 ^b		According to institutional practice	

Abbreviations: C = cycle; CRP = clinical research physician; D = day; DLT = dose-limiting toxicity; dox = doxorubicin; g = grams; ifos = ifosfamide; IRR= infusion-related reaction; IV = intravenous; kg = kilogram; m² = square meters; mg = milligrams; min = minutes; olara = olaratumab.

- a All patients will receive study therapy (olaratumab + doxorubicin/ifosfamide/mesna) for a maximum of 6 cycles, or until a discontinuation criterion is met. Patients who discontinue doxorubicin, ifosfamide and mesna treatment without evidence of disease progression will receive olaratumab as monotherapy until there is evidence of disease progression, death, intolerable toxicity, or other withdrawal criteria are met.
- b If DLT rules (see Section 7.2.2.1) are exceeded in the olaratumab 15-mg/kg cohort, a reduced dose of ifosfamide (7.5 g/m² total dose) will be explored. This reduced dose will be communicated by the Lilly CRP and will be accomplished by omitting the Day 4 dose (that is, ifosfamide will be administered at a dose of 2.5 g/m² on D1, D2 and D3). The Day 4 dose of mesna will be correspondingly omitted. A Loading Dose Cycle of olaratumab (20 mg/kg on Days 1 and 8 of C1, then 15 mg/kg on Days 1 and 8 of subsequent cycles) may also be explored in combination with the reduced dose of ifosfamide.

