Abbreviations: C = cycle; D = day; dox = doxorubicin; hr = hour; ifos = ifosfamide; IG = immunogenicity; min = minute; IRR = infusion-related reaction; obs = observation; olara = olaratumab; PGx = pharmacogenetics; PK = pharmacokinetics.

a Post-infusion is defined as after the completion of the infusion.

b Samples of approximately 3 mL of whole blood will be drawn without anticoagulant for measurement of olaratumab in serum.

- c Samples of approximately 2 mL of whole blood will be drawn into plastic tubes with anticoagulant for measurement of ifosfamide in plasma.
- d Samples of approximately 3 mL of whole blood will be drawn into plastic tubes with anticoagulant for measurement of doxorubicin in plasma.
- e For the immunogenicity assay, approximately 5 mL of whole blood will be drawn into a serum separator tube without anticoagulant to generate serum samples.
- f If a patient experiences an IRR to olaratumab, blood samples for immunogenicity and PK analysis will be taken at the following time points: (1) as soon as possible after the onset of the IRR, (2) at the resolution of the IRR and (3) 30 days (± 3 days) after the IRR.
- g Patients must have sufficient available material from an archived formalin-fixed paraffin-embedded tumor tissue. If such tissue is not available, a newly obtained core or excisional biopsy of a tumor lesion must be performed.
- h Pretreatment samples may be collected any time during the day of the clinical visit, prior to the start of the olaratumab infusion and must be taken prior to administering any premedication.
- i It is highly recommended to draw the PGx sample prior to the first dose of study drug (C1D1); however, it can be collected at a later time point, if necessary.
- j If doxorubicin is administered as a 24 hour infusion, the doxorubicin PK sample should be collected at the same time as the ifosfamide PK sample (that is, approximately 3 to 4 hours after the start of the doxorubicin infusion).
- k For patients who have discontinued doxorubicin/ifosfamide early, these samples may be omitted if there is no other reason for the patient to visit the clinic.
- ^l Should a patient discontinue doxorubicin or ifosfamide, all subsequent PK samples for the corresponding chemotherapeutic agent can be omitted.

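### The Day 4 G-CSF example for reduced-ifosfamide cohorts breaks the protocol's own 24-hour rule when doxorubicin is given as the permitted 24-hour infusion; the rule gives Day 5

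*Protocol*

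**What the plan says.** Protocol 7.8.2 is firm that G-CSF is given: "G-CSFs such as pegfilgrastim must be used at each cycle". The timing rule there, in 7.4.3.2.1 and in the G-CSF row of Table JGDR.2 (Section 2) is the same: "In general, G-CSF products like filgrastim or pegfilgrastim should be administered approximately 24 hours after the completion of cytotoxic chemotherapy". Each of the three places then translates the rule into calendar days: "for example, on Day 5 for patients in full-dose ifosfamide cohorts or Day 4 for patients in reduced-dose ifosfamide cohorts". Ifosfamide cohort is the only thing that changes the day.

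Doxorubicin is given on Days 1, 2 and 3 in every cohort, and 7.6.2 leaves its duration to the site: "Doxorubicin may be administered either as a bolus over 60 minutes or less, or as a 24-hour continuous infusion, depending on institutional protocol". Tables JGDR.2 and JGDR.6 also allow a continuous infusion. Appendix 4, footnote j, sets a separate sampling rule that opens "If doxorubicin is administered as a 24 hour infusion", and it is attached to the Day 1 and Day 3 doses. SAP 5.10 lists a possible safety comparison of the two infusion types.

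In the reduced cohorts (5.1.3; Table JGDR.6, footnote b) ifosfamide is given on Days 1 to 3 only, and the same footnote says of mesna: "The Day 4 dose of mesna will be correspondingly omitted". None of the three G-CSF texts makes an exception for 24-hour doxorubicin.

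**The concern.** The end of chemotherapy is set by whichever cytotoxic drug finishes last. Dropping the Day 4 ifosfamide dose brings that end forward to Day 3 only if doxorubicin also finishes on Day 3. With a 24-hour infusion started on Day 3 it does not. A site that follows the stated day would give G-CSF while doxorubicin is still running, or within hours of its end.

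This would first happen in Cycle 1, which is the DLT window. Febrile neutropenia (Grade 3 or 4) and Grade 4 neutropenia of at least 7 days are DLTs under 7.2.2.1. In the olaratumab 15 mg/kg reduced-ifosfamide cohort, the DLT count decides whether the study halts (Table JGDR.7: 6 of 6, at least 6 of 9, or at least 9 of 15 patients). Neutropenia prophylaxis that is mandatory, and that bears on events counted in that rule, should have unambiguous timing. In these cohorts a mistimed dose would also fall on only one side of the infusion-type comparison in SAP 5.10.

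**Working it through.** **Inputs from the protocol.** G-CSF at about 24 h after the end of chemotherapy (7.8.2). Doxorubicin on Days 1 to 3 (5.1), over 60 minutes or less, or over 24 h (7.6.2). Ifosfamide over 3 h (Table JGDR.6), on Days 1 to 4 at full dose and Days 1 to 3 at reduced dose.

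**Assumption.** Doxorubicin starts at the same clock time *t* on each of its days, with *t* between 08:00 and 16:00. On Day 4 of the full-dose regimen, ifosfamide starts at about *t*.

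**Formula.** End of chemotherapy = the later of the last doxorubicin end and the last ifosfamide end. G-CSF day = the calendar day of that time plus 24 h.

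**The plan's own examples first.**
- Reduced dose, bolus doxorubicin: 1 h of doxorubicin then 3 h of ifosfamide ends on Day 3 at *t* + 4 h. Adding 24 h gives Day 4 at *t* + 4 h, that is 12:00 to 20:00. Day 4 is reproduced.
- Full dose, either infusion type: Day 4 ifosfamide ends at *t* + 3 h, later than a 24-hour doxorubicin infusion ending on Day 4 at *t*. Adding 24 h gives Day 5 at *t* + 3 h, that is 11:00 to 19:00. Day 5 is reproduced.

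**Reduced dose with 24-hour doxorubicin.** The third infusion starts on Day 3 at *t* and ends on Day 4 at *t*. Adding 24 h gives Day 5 at *t*. The calendar day does not depend on *t*, provided the infusion starts on Day 3.

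Measured from the end of that infusion, Day 4 (00:00 to 24:00) runs from −*t* to 24 − *t* hours:

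| Doxorubicin start *t* | Day 4 relative to infusion end | Shortfall from 24 h at the last moment of Day 4 |
|---|---|---|
| 08:00 | −8 h to +16 h | 24 − 16 = 8 h |
| 10:00 | −10 h to +14 h | 24 − 14 = 10 h |
| 16:00 | −16 h to +8 h | 24 − 8 = 16 h |

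A site that counted 24 h from the end of Day 3 ifosfamide (Day 3 at *t* + 3 h, if started alongside doxorubicin) would dose on Day 4 at *t* + 3 h, only 3 h after doxorubicin ends.

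**Other readings of the text.** One uninterrupted three-day infusion also ends on Day 4 at *t*. If ifosfamide must strictly follow doxorubicin, as Table JGDR.6 orders it, Day 3 ifosfamide moves to Day 4 and ends at *t* + 3 h, so chemotherapy ends later still. Both give Day 5.

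**How likely the affected cohorts are to open.** They open if the starting cohort has at least 6 of 9 patients with DLTs, or otherwise at least 9 of 15. The chance is P(X₉ ≥ 6) + Σₖ₌₀⁵ P(X₉ = k) · P(X₆ ≥ 9 − k), where X₉ and X₆ are binomial DLT counts in the first 9 and the next 6 patients:
- true DLT rate 30%: 0.025 + 0.007 = 0.03
- 46%: 0.182 + 0.082 = 0.26
- 70%: 0.730 + 0.161 = 0.89

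The 30% and 70% rates are the scenarios in protocol 10.1. The 46% is the backbone febrile neutropenia rate cited in 5.1, used here only as an assumed DLT rate.

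**How many patients.** If that path runs its full course, it covers two dose-finding cohorts of 15 and a confirmation cohort of 15, that is 45 patients. The number affected ranges from none to all of them, because the share on 24-hour doxorubicin is not stated.

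**The case against.** The strongest reply is that the operative instruction is correct and stands in the same sentence. The days are offered as an illustration, the rule is qualified as general and approximate, and administration is also tied to ASCO and NCCN guidelines. A site that applies the rule reaches Day 5, and dosing during the infusion would mean ignoring the requirement that chemotherapy be complete. The group is also doubly conditional: a reduced cohort must open, and the site must use 24-hour doxorubicin. Nothing in the documents says how far earlier G-CSF would change febrile neutropenia or the duration of neutropenia. The SAP subgroup is optional, and since infusion type follows institutional practice it is already confounded with site.

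Most of this stands, and it limits the weight of the point. No effect on DLT counts or on the halting rule can be quantified, and the SAP comparison is a secondary consideration. It does not remove the error. The example is the only calendar day sites are given, it appears in the Schedule of Activities, and it makes cohort the sole determinant of the day. Allowing for approximation does not stretch 24 hours to cover a dose given during chemotherapy or at most 16 hours after it. The patients concerned are foreseen in the dosing table, the doxorubicin handling section, the sampling footnotes and the SAP.

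**Conclusion.** The concern holds within a narrow scope. For reduced-ifosfamide patients on 24-hour doxorubicin, the stated Day 4 contradicts the protocol's own rule, which gives Day 5. This rests on the third infusion starting on Day 3, as the dosing days and footnote j indicate. The clock times affect only the size of the gap: over the assumed range, even the last moment of Day 4 is 8 to 16 hours too early. The full-dose example and the bolus case are correct. No DLT threshold, sample size or power figure changes. How often a site would follow the example rather than the rule cannot be determined from the documents. The text should be corrected because it is a safety instruction, wrong for a foreseen group, that first applies in the DLT window.

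**What to change.** In the G-CSF row of Table JGDR.2, in 7.4.3.2.1 and in 7.8.2, directly after "Day 4 for patients in reduced-dose ifosfamide cohorts", add: *(Day 5 if doxorubicin is given as a 24-hour infusion)*. The rule and the full-dose example stay as they are.

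The cost is one parenthesis in three places. No new data or procedures are needed, and Appendix 4 already requires infusion start and stop times to be recorded.
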